1.2 Study Purpose

The purpose of this study is to gather confirmatory data on the efficacy and safety of 2% miconazole oil after topical otic administration in subjects with otomycosis, and to fully establish evidence of efficacy for miconazole oil compared to the placebo (mineral oil). A 14-day regimen of twice-daily administration of 2% miconazole oil will be compared with the same treatment regimen using the placebo, mineral oil.

1.3 Inclusion of Subjects with Peanut Allergy

Miconazole oil contains refined peanut oil. Inclusion in this study of subjects with peanut allergy is justified by studies and publications documenting safe use of the refined peanut oil, as well as the FDA approved products containing the refined peanut oil (such as DermOtic, which is the same product as the Derma-Smoothe/FS for which two safety studies were performed in subjects with known hypersensitivity to peanuts) [Yunginger 2001; Paller 2003]. Reports also exist of subjects with known peanut allergy who have continued to safely use products such as Derma-Smoothe/FS even after an anaphylactic reaction to peanuts [Paller 2003]. The refined peanut oil used in the Derma-Smoothe/FS, DermOtic, and miconazole oil products, undergoes refining process to remove the peanut proteins which are generally responsible for allergic reactions to peanuts. Thus, the inclusion of subjects with peanut allergy in this study is not expected to pose an excessive risk to these subjects.

1.4 Compliance with Good Clinical Practice

The investigator and all study staff will conduct the study in compliance with this protocol and FDA regulations, all applicable federal, state, and local laws, rules and regulations relating to the conduct of a clinical study, the ethical principles of the Declaration of Helsinki, and the current International Conference on Harmonisation (ICH) Good Clinical Practice (GCP) guidelines.

2 STUDY OBJECTIVES AND ENDPOINTS

2.1 Objectives

The objectives of the study are to:

- Confirm the efficacy of miconazole oil compared with mineral oil over a 14-day treatment duration in subjects with otomycosis
- Further assess the safety of miconazole oil over a 14-day treatment duration in subjects with otomycosis

2.2 Endpoints

The primary efficacy endpoint is:

- Clinical Cure, defined as score of 0 for fungal elements, and 0 for each of the signs/symptoms of pruritus, aural fullness and debris, at the Test of Cure visit.

The secondary efficacy endpoints are:

- Clinical Cure at the End of Treatment visit with Clinical Cure defined as score = 0 for fungal elements, and score = 0 for each signs/symptoms of otomycosis (debris, pruritus and aural fullness)

- Clinical Clearance at Test of Cure visit with Clinical Clearance defined as score = 0 for fungal elements, and score = 0 or 1 for each signs/symptoms of otomycosis (debris, pruritus and aural fullness)
- Clinical Clearance at End of Treatment visit with Clinical Clearance defined as score = 0 for fungal elements, and score = 0 or 1 for each signs/symptoms of otomycosis (debris, pruritus and aural fullness)
- Modified Clinical Cure at the Test of Cure visit with Modified Clinical Cure defined as score = 0 for fungal elements, and score = 0 or 1 for each of debris and aural fullness
- Modified Clinical Cure at the End of Treatment visit with Modified Clinical Cure defined as score = 0 for fungal elements, and score = 0 or 1 for each debris and aural fullness

The exploratory efficacy endpoint is:

- Mycological culture results through time

2.3 Primary Estimand

The primary estimand will address the following clinical question of interest:

- To establish the efficacy of miconazole oil when taken over a 14-day treatment duration compared with mineral oil in subjects with uncomplicated otomycosis of the external ear only.

This primary estimand is defined as follows:

- Target population: all randomized subjects as defined by the study inclusion / exclusion criteria who are dispensed study drug (ITT population).
- Variable of interest (primary efficacy endpoint): the proportion of subjects who achieve Clinical Cure, defined as score of 0 for fungal elements, and 0 for each of the signs/symptoms of pruritus, aural fullness and debris at the Test of Cure visit
- Intercurrent events (IcE)
 1. Discontinuation of study treatment due to AE unrelated to study drug
 2. Discontinuation of study treatment due to AE related to study drug
 3. Discontinuation of study treatment due to lack of efficacy
 4. Use of rescue medication prior to the Test of Cure visit

For each above IcE, a composite strategy will be taken where subjects with any of the above IcEs will be considered to have not achieved Clinical Cure.

- Population-level summary: the difference in proportions in Clinical Cure at the Test of Cure visit between the miconazole group and the mineral oil group.

3 STUDY DESIGN

This study is a randomized, double-blind, parallel-group study to be conducted at up to 8 study centers in the US. An estimated 110 male or female subjects with otomycosis will receive study drug. Subjects will be randomly assigned in a 1:1 ratio within study site to receive miconazole oil or mineral oil for 14 days [administered as 5 drops per ear at ~30 mg per drop instilled into the external ear canal of the ear(s) affected by otomycosis]. Both the subject and the investigator and study staff will be blinded as to the contents of the study drug.

At Screening/Baseline (Day 1), potentially eligible subjects will provide informed consent, and subjects will undergo screening evaluations to include a condensed physical examination, an assessment of the signs and symptoms of otomycosis (pruritus, debris, visual examination for presence of fungal elements, and aural fullness), and an evaluation of medical history. Urine will be obtained for pregnancy screening in female subjects of childbearing potential. Prior and concomitant medications will be reported. Subjects with positive signs and symptoms of otomycosis and who meet all other eligibility criteria will be entered into the study. A fungal culture of the affected ear(s) will be taken, then debris will be cleaned from the affected ear(s) following the site's normal procedures. The subject will then begin treatment with study drug. The subject or caregiver will instill the first dose of study drug at the site, under the supervision of the investigator or site personnel. Adverse events (AEs) will be assessed. The subject will then leave the clinic and continue to administer the study drug twice per day as instructed. Subjects will be instructed to avoid getting water in the ear, to consider drying excessive water in the ear by using a blow dryer, and to place a Vaseline-impregnated cotton ball over the affected ear(s) to help keep water out of the ear while bathing or showering.

Subjects will continue to administer the study drug twice per day, up through Day 14, following the same instructions as provided at the Screening/Baseline Visit on Day 1. Subjects will then return to the clinic on Day 15 for the End of Treatment Visit, at which time a clinical evaluation of the signs and symptoms of otomycosis will be performed. AEs and concomitant medications will also be assessed, and the subject will return all unused study drug.

Subjects will return to the clinic on Day 22 for the Test of Cure Visit, at which time an assessment of clinical signs and symptoms of otomycosis and fungal culture of the affected ear(s) will be performed. AEs and concomitant medications will also be assessed. A urine pregnancy test will be performed in women of childbearing potential. Results from the fungal culture will not be used to assess primary or secondary efficacy endpoints. All fungal results will be summarized.

Efficacy assessments will include assessments of clinical signs and symptoms of otomycosis. In cases of bilateral otomycosis, both ears will be treated and evaluated by the investigator, but only one ear will be used as the study ear for efficacy analyses, the designation of which will be performed at the end of the study in accordance with the following: (1) If only one ear has clinical signs/symptoms at Screening/Baseline, that ear will be used as the study ear for efficacy analyses; (2) If both ears have clinical signs/symptoms at Screening/Baseline, the ear with the worse infection at Screening/Baseline as assessed by the investigator, will be used as the study ear for efficacy analyses; (3) If both ears are determined by the investigator to have the same

degree of infection at Screening/Baseline, the left ear will be used as the study ear for the purposes of efficacy analyses.

Safety assessments will include AEs.

For subjects who did not improve or had received the placebo, optional rescue treatment may be provided at the end of the study.

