
Subjects will continue to administer the study drug twice per day, up through Day 14, following the same instructions as provided at the Screening/Baseline Visit on Day 1. Subjects will return to the clinic on Day 15 for the End of Treatment Visit, at which time a clinical evaluation of the signs and symptoms of otomycosis will be performed. AEs and concomitant medications will also be assessed, and the subject will return all unused study drug.
 
Subjects will return to the clinic on Day 22 for the Test of Cure Visit, at which time a clinical evaluation of the signs and symptoms of otomycosis and a fungal culture of the affected ear(s) will be performed. AEs and concomitant medications will also be assessed. A urine pregnancy test will be performed in women of childbearing potential.

Study Visits: Screening/Baseline (1 visit); End of Treatment (1 visit); Test of Cure (1 visit)
Efficacy Evaluations: 
Clinical signs and symptoms of otomycosis (pruritus; debris; presence of fungal elements; aural fullness)
Safety Evaluations: 
AEs
Key Inclusion Criteria: 
Male or non-pregnant, non-lactating females with a clinical diagnosis of uncomplicated otomycosis of the external ear only, with an intact tympanic membrane, who are in general good health as determined by medical examination and medical history, and who are free of clinically significant disease, including diabetes mellitus, that is not well-controlled or that could interfere with the study, will be included in the study. In each ear to be treated with study drug, subjects must have a visual presence of fungal elements and must also have the following signs or symptoms of otomycosis: pruritus ≥ 2; debris ≥ 2; and aural fullness ≥ 2.

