Endpoints: Primary Efficacy Endpoint 
Percentage of subjects with "Clinical Cure," defined as the score of 0 for fungal elements, and score of 0 for signs and symptoms of otomycosis (pruritus, debris, and aural fullness). Safety Endpoint 
Percentage of subjects with treatment-emergent adverse events (TEAEs).

Name of Sponsor/Company: Hill Dermaceuticals, Inc.**Name of Finished Product:** Miconazole oil**Name of Active Ingredient:** 2% miconazole**Statistical Analyses:**

Descriptive statistics will be presented for the percentages of subjects by treatment group with Clinical Cure in the study ear at each evaluation. Descriptive statistics will also be presented for the percentages of subjects by treatment group with each sign or symptom of otomycosis in the study ear at each evaluation. Descriptive statistics will include the number and percentage of subjects in each category.

In cases of bilateral otomycosis, the ear with the worse infection at Screening/Baseline, as assessed by the investigator based on clinical signs and symptoms, will be used as the study ear for efficacy analyses. If both ears are determined by the investigator to have the same degree of infection at Screening/Baseline, the left ear will be used as the study ear for the purposes of efficacy analyses.

For the primary efficacy endpoint, percentages of subjects with Clinical Cure at the Test of Cure Visit will be compared using a Cochran-Mantel-Haenszel (CMH) exact test stratified by clinical site with a 2-sided significance level of 0.05. Comparisons will be conducted in a similar manner between the miconazole oil and mineral oil (placebo) groups for the secondary endpoints. Missing data will be imputed as treatment failures for the primary and secondary efficacy analyses; missing data otherwise will not be imputed.

The primary population for all efficacy analyses will be the ITT population, defined as all subjects who were randomized, dispensed study drug, and with a clinical diagnosis of otomycosis.

The primary population for all safety analyses will be the safety population, defined as all randomized subjects who received at least one dose of study drug and had at least one post-Baseline safety assessment.

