4 STUDY SUBJECTS

4.1 Inclusion Criteria

In order to be eligible for the study, subjects must meet all of the following criteria:

1. Male or non-pregnant, non-lactating females
2. Diagnosis of uncomplicated otomycosis of the external ear only, in the ear(s) that will be treated with study drug, with a score for fungal elements of 1 in each ear to be treated with study drug (see Section 7.4 for definitions of the scores for each of the otomycosis signs and symptoms). Subjects must also have the following signs and symptoms of otomycosis in the study ear: pruritus ≥ 2 ; debris ≥ 2 ; and aural fullness ≥ 2 .
3. General good health as determined by medical examination and medical history, and who are free of clinically significant disease, including diabetes mellitus that is not well-controlled or that could interfere with the study
4. Females of childbearing potential must have had a negative urine pregnancy test at Screening/Baseline and must agree to use an effective method of contraception (as defined in Section 8.5) from Screening/Baseline up through the End of Treatment visit (see Section 6). Females of childbearing potential include any female who has experienced menarche and who has not undergone successful surgical sterilization (hysterectomy, bilateral tubal ligation or bilateral oophorectomy) or is not postmenopausal (defined as amenorrhea >12 consecutive months). Females who are using oral, implanted, or injectable contraceptive hormones, an intrauterine device (IUD), barrier methods (diaphragm, condoms, spermicide) to prevent pregnancy, practicing abstinence or where partner is sterile (e.g., vasectomy), should be considered to be of childbearing potential
5. Subjects and/or their caregivers (as appropriate for the age of the subject) must have full legal capacity to volunteer
6. Subjects and/or their caregivers must have completed an appropriately administered institutional review board (IRB)-approved informed consent and assent (as applicable) prior to any study related procedures
7. Subjects and their caregivers (as applicable) must agree to comply with all requirements of the protocol

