8. For subjects with only one ear meeting all study eligibility criteria, the subject will be eligible for the study, and the ear meeting all eligibility criteria will be treated with study drug and considered to be the study ear for the purposes of study evaluations. In case of bilateral otomycosis in which at least one ear meet all study eligibility criteria, the subject will be eligible for the study, both ears may be treated with study drug provided that both ears have a score of 1 for fungal elements, and the worse ear will be considered to be the study ear for the purposes of study evaluations. If both ears meet study eligibility criteria and are determined by the investigator to have the same degree of infection at Screening/Baseline, the left ear will be considered to be the study ear for the purposes of study evaluations.

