6.8. Safety Evaluation

6.8.1. Extent of Exposure

The extent of exposure to study drug in each treatment group will be summarized by total number of days of exposure, total number of doses, number of missed doses and number and percentage of subjects who are compliant. A subject will be considered compliant with the dosing regimen if the subject applied 80% to 120% of the expected number of doses while enrolled in the study.

Days of exposure = Date of Last Dose – Date of First Dose + 1

Total Number of Doses:

$$2 * (\text{Date of Last Dose} - \text{Date of First Dose} + 1) - (\text{Number of study ear doses missed as collected on the case report form (CRF)}) + (\text{Number of study ear extra doses as collected on the CRF})$$

Total Number of Expected Doses = 28

If a subject discontinues from the study early before the End of Treatment Visit, the number of expected doses will be calculated to the later of the last visit date or date of last dose. If the total number of expected doses exceeds 28 then the total number of expected doses will be set to 28.

Compliance will be calculated as a percentage as 100 times the total number of doses divided by the total number of expected doses.

Extent of exposure summaries will be provided using the Safety population.

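### In bilateral cases the study ear is designated at the end of the study by an unscored, unrecorded judgement of which ear was worse at baseline, and the documents conflict on whether that ear must be eligible.

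*Protocol*

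**What the plan says.** **Timing.** Protocol section 3 states that in bilateral cases "both ears will be treated and evaluated by the investigator, but only one ear will be used as the study ear", and then "the designation of which will be performed at the end of the study in accordance with the following". SAP section 4.1 repeats this. SAP section 6.7.1 sends bilateral subjects in the primary analysis to that rule.

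**Criterion.** If both ears show signs or symptoms, "the ear with the worse infection at Screening/Baseline as assessed by the investigator, will be used as the study ear for efficacy analyses". The Protocol synopsis (Statistical Analyses) gives the basis slightly more fully: the worse ear, "as assessed by the investigator based on clinical signs and symptoms, will be used as the study ear for efficacy analyses". No document says how the separate scores combine into worse. Ties go to the left ear.

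**Eligibility of the chosen ear.**
- Protocol section 4.1, item 2, sets minimum scores of 2 for pruritus, debris and aural fullness: "Subjects must also have the following signs and symptoms of otomycosis in the study ear".
- Item 8 admits a bilateral subject when at least one ear qualifies. It allows both ears to be treated if both have a fungal score of 1, and adds that "the worse ear will be considered to be the study ear for the purposes of study evaluations".
- The synopsis (Key Inclusion Criteria) is stricter: "In each ear to be treated with study drug, subjects must have a visual presence of fungal elements". The same sentence applies the three score thresholds to each treated ear.

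**The concern.** One ear per subject supplies Clinical Cure, so in bilateral disease the choice of ear can decide the outcome whenever one ear is cured and the other is not. A choice made after both outcomes are known should leave no discretion. Here worse rests on a judgement that no Day 1 step records: neither the study schedule (Protocol section 6.1) nor the Screening/Baseline procedures (section 6.2.1) list it. A late judgement could not be checked against a contemporaneous one.

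The second problem is that the rule can return different ears depending on which section is followed. A site using item 2 and a programmer using SAP section 4.1 could score the same subject on different ears, one of them below the entry thresholds.

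**Working it through.** **1. The plan's own figure.** The plan gives no figure for bilateral disease or for agreement between ears. Its only related figure is 80% power at 55 per arm for 35% versus 10% (Protocol section 10.3). Exact enumeration of Fisher's test gives 85.5%. That gap is a separate matter: the study-ear rule enters no sample-size input.

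**2. Can the written rule return an ear below threshold?** Let both ears have fungal score 1, so that item 8 allows both to be treated. Score each ear 0 to 3 on pruritus, debris and aural fullness, giving 4³ = 64 triples. Eligible triples (all at least 2): 2³ = 8. Ineligible: 64 − 8 = 56. Pairs of one eligible and one ineligible ear: 8 × 56 = 448. Rank severity by the sum of the three scores (an assumption, as the plan has no ranking):
- Ineligible ear strictly worse: 3 pairs. These are 2/2/2 (sum 6) against 3/3/1 in any order (sum 7).
- Tie: 18 pairs. At sum 6, 2/2/2 meets the six orders of 3/2/1 and the three orders of 3/3/0 (9 pairs). At sum 7, the three orders of 3/2/2 meet the three orders of 3/3/1 (9 pairs).

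The sections then give different answers:

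| Text | Ineligible ear worse | Tie, only one ear eligible |
|---|---|---|
| Protocol 3, 10.5.1; SAP 4.1 | ineligible ear | left ear, eligible or not |
| Protocol 4.1, item 8 | worse ear, so ineligible | not covered: its left-ear rule needs both ears eligible |
| Protocol 4.1, item 2 | barred | ineligible ear barred |
| Synopsis, Key Inclusion Criteria | second ear not treatable | second ear not treatable |

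These are counts of score patterns, not frequencies among patients.

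**3. How far could an outcome-informed choice move the result?** Take the extreme in which the cured ear is always chosen. Let *b* be the bilateral share, *ρ* the between-ear correlation of cure and *p* the per-ear cure rate. The chance that at least one of two ears is cured is 2p − [p² + ρp(1−p)], so the arm's rate becomes

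p + b·p(1−p)·(1−ρ).

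Neither *b* nor *ρ* is in the documents. I assume *b* = 5% to 40% (110 × 0.05 = 5.5 to 110 × 0.40 = 44 subjects) and *ρ* = 0.3 to 0.9.
- From 35%: lowest 0.35 + 0.05 × 0.2275 × 0.1 = 35.1%; highest 0.35 + 0.40 × 0.2275 × 0.7 = 41.4%.
- From 10%: lowest 0.10 + 0.05 × 0.09 × 0.1 = 10.0%; highest 0.10 + 0.40 × 0.09 × 0.7 = 12.5%.
- Difference: from 25 points to at most 25 + 100 × 0.40 × 0.7 × (0.2275 − 0.09) = 28.85 points.

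Type I error was found by exact enumeration at 55 per arm, with a null cure rate of 21.9% (14 of 64, the vehicle arm of the first Phase 3 study, Protocol section 1.1):

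| Scenario | Chi-square | Fisher |
|---|---|---|
| No outcome-informed choice | 0.051 | 0.028 |
| Same choice in both arms | 0.050–0.051 | 0.028–0.030 |
| Blind fails completely, one arm only benefits | 0.051–0.090 | 0.028–0.058 |

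The tests are unstratified, whereas the SAP uses a CMH test by analysis center. The table shows scale, not exact levels.

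**The case against.** The strongest reply is that assessing which ear was worse and designating the study ear are two separate steps. Only the second is placed at the end, and every input to it is a baseline input. Each treated ear is scored on four scales on Day 1. Protocol section 9.1.1 has the less severe ear dosed first, so some severity ranking is already needed that day. The investigator and staff are blinded (section 9.3). All of this stands, and it limits the concern to late discretion over a baseline judgement. It does not close the gap: the ranking has no rule and is not recorded, and who makes the designation is not stated.

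Stronger readings that the documents do not support:
- *The plan selects the ear on its outcome, so type I error is inflated.* The written criterion is baseline severity. Even if it were ignored in the same way in both arms, type I error would stay near nominal.
- *Allocation is known when the ear is designated*, because section 3 mentions optional end-of-study rescue for subjects who had received placebo. No order between unblinding and designation is given, so this is an open question, not evidence that the blind fails.
- *One switched ear decides the trial.* At 19 versus 9 cures the chi-square p is 0.029, and at 19 versus 10 it is 0.0515, but this pair was picked at the boundary. Near the planned rates (35% and 10% of 55 are 19.25 and 5.5), 19 versus 6 gives about 0.003, and one changed outcome does not matter.
- *The plan intends ineligible study ears, or makes such subjects per-protocol violators.* Item 2 and the synopsis bar an ineligible study ear, while item 8 declares the subject eligible. The texts contradict each other and no intention is settled.
- *The CRF proves the ear is known from Day 1*, because SAP section 6.8.1 uses the "Number of study ear doses missed as collected on the case report form". Collecting doses for each ear and selecting later fits equally well.

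**Conclusion.** The point holds as a gap in specification and a contradiction between sections; it is not a demonstrated bias. End-of-study designation is explicit in both documents, worse is unscored, and no Day 1 record is specified.

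With the blind intact, an outcome-informed choice could move cure rates (at the extreme, 35% to 41.4% and 10% to 12.5%). It could also enlarge a real difference, because the analysis would no longer describe the ear that was worse at baseline. It would not create a difference where none exists. Inflation up to 0.090 needs complete failure of the blind, benefit to one arm only, a 40% bilateral share and a correlation of 0.3, all assumed. How many subjects are affected cannot be determined from the documents.

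The eligibility conflict is certain as text. Its frequency is unknown, and the 3 and 18 score pairs depend on ranking by sum. The change is worth making because it protects the primary endpoint at almost no cost.

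**What to change.** 1. Replace end-of-study designation with designation at Screening/Baseline, before randomization, recorded and locked on the baseline eCRF. For subjects already enrolled, derive the ear by program from the recorded baseline scores before unblinding.
2. Choose only among ears that meet the ear-level eligibility criteria. If both qualify, apply a prespecified rule to the baseline scores, for example the higher sum of pruritus, debris and aural fullness. The equal-weight sum is one option; what matters is that the rule is fixed in advance. Ties between eligible ears go to the left ear.
3. Use the same text in the Protocol synopsis, sections 3, 4.1 (items 2 and 8) and 10.5.1, and in SAP sections 4.1 and 6.7.1.
4. The synopsis, Protocol sections 3 and 4.1 (item 8) and SAP section 6.7.1 also differ on which ears may be treated. The sponsor must reconcile them; no position is taken here on which is right.

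Cost: one eCRF field or a short derivation, and aligned wording. No added visits or subjects, and no change to the sample size.
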